### Cytarabine

Day 4-6 (10) 100 - 1000 mg/sqm (according to dose level)

Cytarabine will be given at increasing doses and should be administered after venetoclax intake. In the dose escalation part of the trial, cytarabine will be given at increasing doses as outlined in Table 1 starting from day 4. Cytarabine will be administered as continuous infusion in dose levels -1 and 1, by IV infusion over 2 hours twice daily in dose levels 2 and 3.

### Mitoxantrone

Day 6-8 10 mg/m^2 IV over 1 hour

Mitoxantrone will be administered by IV infusion over 1 hour on day 6, 7 and 8 parallel to cytarabine in cohort -1 and 1, after cytarabine infusion in cohorts 2 and 3 (see [Figure 2](#)).

## **5.4.2 Treatment schedule in the expansion part of the study (phase II)**

### Venetoclax

Venetoclax will start on day 1 and continue until day 14 (10) with a ramp up period as outlined in Table 2 in section [5.4.1](#).

In case of co-administration with posaconazole and other strong and moderate CYP3A inhibitors, dose modifications of venetoclax are required as described in section [5.5](#).

### Cytarabine

Cytarabine will be given at the MTD or highest tolerable dose determined in the dose escalation part. Administration conditions will be identical to the dose escalation part of the trial (see [5.4.1](#)).

### Mitoxantrone

Day 6-8 10 mg/m^2 IV over 1 hour

Mitoxantrone will be administered by IV infusion over 1 hour on day 6, 7 and 8.

## **5.4.3 Treatment schedule in the maintenance therapy**

Patients who achieve a CR/CRp with ANC recovery ( $ANC \geq 1000/\mu L \geq 1 \times 10^9/L$ ) may receive venetoclax maintenance treatment up to twelve 28-day cycles if they have no other post-remission treatment options (e.g. auto/allo-TX, chemo-consolidation therapy etc.).

Venetoclax will be given at dose 400 mg QD per os as continuous treatment starting within 14 days after the End of Treatment assessment of previous treatment phase up to 12 cycles. Duration of one cycle is 28 days.

If co-administration with strong and moderate CYP3A inhibitors daily dose will be reduced according to section [5.5](#).

#### 5.4.4 Dose modifications during V-MAC in expansion and maintenance treatment

The following dose reduction rules shall be applied in case toxicities occur.

In case of either one of these toxicities, venetoclax shall be stopped and re-started according to the recommended dose modifications in Table 3 and Table 4. If co-administration of strong or moderate CYP3A inhibitors, venetoclax dose modification has to be done according to [Table 5](#) and [Table 6](#).

In maintenance therapy, dose reductions according to [Table 3](#), [Table 4](#), [Table 5](#), [Table 6](#) are necessary if either one of the below occurs in patients with CRp:

- ANC falls <1000/ $\mu$ L or
- PLT count falls <50,000/ $\mu$ L or
- Toxicities grade  $\geq$  3

Table 3: Recommended Dose Modifications for Toxicities during V-MAC in expansion and maintenance

Event	Occurrence	Action
Non-Hematologic Toxicities		
Grade 3 or 4 non-hematologic toxicities	1 st occurrence	Interrupt venetoclax. Once the toxicity has resolved to Grade 1 or baseline level, venetoclax therapy may be resumed at the same dose. No dose modification is required.
	2 nd and subsequent occurrences	Interrupt venetoclax. Follow dose reduction guidelines in Table 4 when resuming treatment with venetoclax after event has resolved to grade 1.

Hematologic Toxicities (only during maintenance)		
Grade 3 or 4 neutropenia with infection or fever; or Grade 4 hematologic toxicities (except lymphopenia)	1 st occurrence	Interrupt venetoclax.  To reduce the infection risks associated with neutropenia, granulocyte-colony stimulating factor (G-CSF) may be administered with venetoclax if clinically indicated.  Once the toxicity has resolved to Grade 1 or level on day 1 of maintenance, venetoclax therapy may be resumed at the same dose.
	2 nd and subsequent occurrences	Interrupt venetoclax. Consider using G-CSF as clinically indicated. Follow dose reduction guidelines in Table 4 when resuming treatment with venetoclax after event has resolved to Grade 1 or on day 1 of maintenance.

Table 4: Dose Modification for Toxicity during Venetoclax Treatment

Dose at interruption, mg	Restart dose, mg
400	300
300	200
200	100
100	50
50	Stop study drug permanently

Table 5: Dose Modification for Toxicity during Venetoclax Treatment in case of **Co-medication with strong CYP3A inhibitors**

Dose at interruption, mg	Restart dose, mg
100	50
50	20
20	10
10	Stop study drug permanently

Table 6: Dose Modification for Toxicity during Venetoclax Treatment in case of **Co-medication with moderate CYP3A inhibitors**

Dose at interruption, mg	Restart dose, mg
200	100
100	50
50	20
20	10
10	Stop study drug permanently

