**Complete remission with incomplete platelet recovery (CRp):**

All CR criteria are fulfilled except for residual thrombocytopenia (platelet count  $\leq 100.000/\mu\text{l}$ ).

**Treatment Failure:**Resistant Disease:

Failure to achieve CR or CRi only includes patients surviving  $\geq 7$  days following completion of initial treatment, with evidence of persistent leukemia by blood and/or bone marrow examination

Morphologic relapse:

Reappearance of blasts in PB or bone marrow blasts  $\geq 5\%$  after achievement of complete remission or occurrence of extramedullary disease

Molecular relapse

If MRD can be assessed in the individual patient by multicolour flow cytometry and/or PCR methodology, the patient achieves MRD negative status in CR, the reoccurrence of the previously identified MRD marker in a patient with CR defines a molecular relapse.

Death in aplasia:

Deaths occurring  $\geq 7$  days following completion of initial treatment while cytopenic; with an aplastic or hypoplastic bone marrow obtained within 7 days of death, without evidence of persistent leukemia

Death from indeterminate cause:

Deaths occurring before completion of therapy, or  $< 7$  days following its completion; or deaths occurring  $\geq 7$  days following completion of initial therapy with no blasts in the blood, but no bone marrow examination available

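### Section 5.4.4: the maintenance dose-reduction list for CRp patients names events for which Table 3 has no row, and it leaves the first-event action and the platelet trigger unclear

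*Protocol*

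**What the plan says.** Section 5.4.4 opens by telling sites to halt and restart venetoclax following Tables 3 and 4, with Tables 5 and 6 for patients on CYP3A inhibitors. A sentence specific to maintenance then says that reductions following Tables 3 to 6 "are necessary if either one of the below occurs in patients with CRp". The list has three entries: "ANC falls <1000" per µL, "PLT count falls <50,000" per µL, and "Toxicities grade $\geq$ 3".

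Table 3 covers the same phase. Its hematologic part, marked as applying only in maintenance, is triggered by "Grade 3 or 4 neutropenia with infection or fever; or Grade 4 hematologic toxicities (except lymphopenia"). At a first hematologic event venetoclax is interrupted, and then: "Once the toxicity has resolved to Grade 1 or level on day 1 of maintenance, venetoclax therapy may be resumed at the same dose". At a first grade 3 or 4 non-hematologic event it is interrupted until resolution, after which "venetoclax therapy may be resumed at the same dose. No dose modification is required". The stepwise reductions of Table 4 start at the second occurrence.

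Section 5.4.3 admits patients in CR and in CRp to maintenance, provided ANC is at least 1 x 10^9/L. Section 6.4.2.2 defines CRp thus: "All CR criteria are fulfilled except for residual thrombocytopenia", meaning platelets at or below 100,000/µL, with no lower bound.

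**The concern.** The list and the table stand in one section, govern one drug in one phase, and the list sends the reader to the table. If the table does not contain the event that sent the reader there, the instruction cannot be carried out as written. If the table does contain it but gives an action other than reduction, the site must decide which wording governs.

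At stake are consistent handling of toxicity in patients who may take venetoclax for up to twelve 28-day cycles, and the meaning of the maintenance summaries of dose, interruptions and adverse events. With three phase I sites and seven more for expansion (section 3.6), up to ten sites would be interpreting the section for themselves.

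**Working it through.** No arithmetic underlies the main point, and the plan gives no figure to reproduce. The check sets the list beside Table 3.

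**Inputs.** List and Table 3: section 5.4.4. Grade 4 limits: section 3.2 (DLT definition), ANC below 0.5 x 10^9/L (500/µL) and platelets below 25 x 10^9/L (25,000/µL). Maintenance population: section 5.4.3. CRp: section 6.4.2.2. It is assumed that the DLT limits also describe grade 4 in maintenance.

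**Comparison for a CRp patient in maintenance.**

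| Event | List in the text | Table 3 |
|---|---|---|
| ANC 500-999/µL, no fever or infection | Trigger | No row: not grade 4, and the grade 3 neutropenia entry requires fever or infection |
| Platelets 25,000-49,999/µL | Trigger | No row: not grade 4 |
| Other grade 3 hematologic toxicity, e.g. anemia | Trigger (grade 3 or higher) | No row: only grade 4 counts |
| Grade 3-4 lymphopenia | Trigger (grade 3 or higher) | No row: lymphopenia is excepted |
| First grade 3-4 neutropenia with fever or infection, or first other grade 4 hematologic event | Reduction necessary | Interrupt, then same dose allowed |
| First grade 3-4 non-hematologic event | Reduction necessary | Interrupt, then same dose, no modification |
| Second or later listed event | Reduction necessary | Interrupt, then reduce by Table 4 |

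The first four rows are gaps: the list points to Table 3, and Table 3 is silent. The next two differ in the action after interruption. Only the last agrees on both trigger and action.

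**Population.** The list names CRp; Table 3 names no remission category. Take an ANC of 700/µL without fever or infection. In CRp it meets the list but finds no row in Table 3. In CR it meets neither.

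**Platelets at entry.** Entry sets an ANC threshold but no platelet threshold, and CRp has no lower platelet bound, so a patient may start below 50,000/µL. The list's verb is *falls*. It does not say whether a count already below the limit, or a further drop from there, is a trigger. Table 3 does allow for a low starting count, because hematologic recovery may be to the level on day 1 of maintenance. The list makes no such allowance.

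**What the first-event wording could change.** Table 4 runs 400, 300, 200, 100, 50, stop: four reductions, then permanent discontinuation. If every event reduces the dose, discontinuation comes at event 4 + 1 = 5. If the first event is exempt, it comes at event 1 + 4 + 1 = 6. This assumes a 400 mg start, no CYP3A inhibitor, and all of a patient's events counted in one sequence.

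**The case against.** The best defence is that the text sets no free-standing rule. It calls for reductions following the tables, and the section's opening sentence says to stop and restart as Tables 3 and 4 direct. On that reading Table 3 governs: a first event follows its first-occurrence row, and *reductions* is loose wording for *modifications*. Both places also agree that the drug is interrupted at a listed event. This is a fair reading, and it removes the first-event conflict. It does not fill the four gaps, because deferring to Table 3 leaves those events without any instruction.

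A second defence is that the list may be a deliberate extra rule for patients who begin with residual thrombocytopenia. Narrower scope is not a contradiction in itself, and that stands. The section does not state that intent, however, and a separate CRp rule would still need an action for the events that Table 3 omits.

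Third, maintenance is optional and only for patients without another post-remission option, the non-primary analyses are descriptive, and dose and interruptions are reported for each drug. Differences in dosing would therefore be partly visible. That limits the consequence without making the section executable.

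A reader might infer more than this supports. One inference is that text and table contradict each other outright at every first grade 3-4 event. The cross-reference to Table 3 makes that only one of two readings, and the list reaches only CRp patients. Another is that a CRp patient may enter maintenance already in breach of the platelet rule. *Falls* does not clearly say so; this is an ambiguity in the list, not a conflict with Table 3.

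**Conclusion.** The point holds as an internal inconsistency of wording. Firmest is the trigger mismatch: four classes of event call for a reduction under the list and have no row in the table it cites. The platelet and ANC ranges rest on applying the protocol's DLT grade 4 limits to maintenance. Three lesser points are unclear rather than contradictory: the action at a first listed event in CRp, whether the list is meant for CRp alone, and how the platelet trigger treats a low starting count.

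The effect is confined to maintenance. Sites could interrupt or dose differently for the same event, and the exposure and safety summaries would then carry some site interpretation along with tolerability. The documents do not show that these data would be uninterpretable. The primary CR/CRi analysis and its sample size of 42 are untouched, because remission is assessed on days 28-45, before maintenance begins. The matter should be corrected because it bears on patient safety and costs little to put right.

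**What to change.** The sponsor should reconcile the maintenance list in section 5.4.4 with Table 3 on three things: which events are triggers, which patients each rule covers, and what happens at a first occurrence. Each trigger should lead to a stated action. If a separate rule for CRp is intended, the section should say so; whether CR and CRp share one rule is the sponsor's clinical decision. The section should also state how the platelet trigger applies to a patient already below 50,000/µL on day 1 of maintenance. This review takes no position on which thresholds or actions are right.

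The cost is wording in a protocol amendment, with the ethics committee and authority approval of section 12 if the change significantly affects patient safety. Sample size and the primary analysis do not change.

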#### 5.4.5 Prophylaxis and Management of Tumor Lysis Syndrome (TLS)

There is a potential for TLS in all subjects with AML, especially in those with elevated pretreatment LDH levels, elevated leukocyte count, renal dysfunction and dehydration. To mitigate the risk for TLS (Coiffier et al., J Clin Oncol 2008), subjects will receive tumor lysis prophylaxis, including hydration (e.g., oral, intravenous) and treatment with an agent to reduce the uric acid level (e.g., allopurinol, rasburicase) (Coiffier et al., J Clin Oncol 2008, Cairo et al., Br J Haematol 2004) prior to and during the ramp up period during escalation part. For subjects who had dose delay or interruptions, TLS prophylactic measures may need to be implemented based on the disease status prior to resuming treatment.

##### TLS Prophylaxis and Management in Escalation part:

TLS prophylaxis must be initiated in all such subjects prior to the first venetoclax dose or first new escalated dose as described below.

- Hospitalization (required) starting the night before the first dose of venetoclax and for a minimum of 24 hours after reaching the target dose of 400 mg venetoclax.
- An oral agent to reduce the uric acid level (e.g., allopurinol) to be initiated at least 72 hours prior to dosing. Treatment may need to be continued for up to 28 days based on the ongoing risk of TLS development. Subjects allergic to or otherwise unable to receive allopurinol must use another uric acid reducer starting at least 72 hours prior to dosing or rasburicase on the day of treatment (prior to venetoclax dosing).
- Oral hydration (approximately 1.5 to 2 liters as tolerated) per day starting from at least 24 hours prior to first dose or any dose escalation during ramp up.
- Intravenous hydration must be started upon admission or the night prior to beginning treatment with a target of approximately 2 L per day or as clinically appropriate and continued during

hospitalization. Urine output must be monitored. Diuretics may be used per investigator discretion.

- TLS chemistry tests on the first day of venetoclax dosing and each day of a new dose at pre-dose (within 4 hours prior to dosing), 6-8 hours and 24 ( $\pm$  2) hours post-dose. Additional laboratory assessments may be performed, per investigator discretion, post-dose during ramp up and up to 48 hours after reaching the target dose if clinically indicated.
- TLS chemistry test results (calcium, inorganic phosphorus, potassium, uric acid, and creatinine) must be reviewed by the investigator in real time and prior to the subject's next dose of venetoclax to ensure appropriate subject management.
- If any clinically significant laboratory changes are observed within the first 24 hours after initiation of dosing or after a dose escalation during ramp up, see [Appendix 2](#) (Recommendations for Initial Management of Electrolyte Abnormalities and Prevention of Tumor Lysis Syndrome [TLS]) for management guidelines. Refer to table in [Appendix 3](#) for definitions of laboratory and clinical TLS.
- If a subject meets criteria for clinically significant laboratory TLS, no additional venetoclax dose should be administered until resolution.
  - Prophylactic reductions of potassium, inorganic phosphorus and/or uric acid above normal range prior to beginning dosing are recommended.

For continued dosing of venetoclax, monitor for evidence of TLS during treatment, and manage abnormalities in serum creatinine, uric acid and electrolytes promptly. For subjects at higher risk (i.e., circulating blasts), more intensive measures should be considered. Refer to [Appendix 2](#) for a special sample handling procedure that must be followed to avoid ex vivo uric acid degradation in the presence of rasburicase.

If the chemical changes and laboratory TLS have not resolved within 24 hours, the continuation of venetoclax has to be discussed between the investigator and the Coordinating Investigator.

#### TLS Prophylaxis and Management in the Expansion part

Safety data from the 94 subjects treated in 3 AML studies demonstrated no events of TLS; 32 subjects in monotherapy study (Study M14-212) and 22 subjects in a combination study (Study M14-387) using low dose cytarabine. Based on this data, simplification of TLS prophylaxis and management will be followed for subjects enrolled into the expansion stage.

All subjects enrolled into the expansion part will need TLS prophylaxis and monitoring. The minimum requirements for TLS prophylaxis and management for subjects enrolled into the

expansion part are shown below. All other prophylaxis and monitoring procedures for TLS will be done as per institutional/regional standards:

- All subjects will be hospitalized on or before Day 1 of study treatment (V-MAC) prior to administration of the first dose of study venetoclax and remain in the hospital at least for 24 hours after reaching the target dose of 400 mg venetoclax.
- Administration of uric acid reducing agent, adequate oral and intravenous hydration while monitoring the fluid status of the subject prior to and during the ramp up of venetoclax will be based on regional standards or institutional guidelines.
- TLS chemistry tests are to be drawn (calcium, inorganic phosphorus, potassium, uric acid, and creatinine) on the first day of venetoclax dosing and on each day of a new dose at pre-dose (within 4 hours prior to dosing), 6-8 and 24 ( $\pm$  2) hours post dose. Additional laboratory assessments may be performed, per investigator discretion, post-dose during ramp up and up to 48 hours after reaching target dose if clinically indicated.
- Abnormal chemistry test results should be corrected promptly.
- If a subject meets criteria for clinically significant laboratory or clinical TLS, no additional venetoclax dose should be administered until resolution.
  - Prophylactic reductions of potassium, inorganic phosphorus and/or uric acid above normal range are recommended prior to beginning study treatment and continue based on the ongoing risk of TLS.

For continued dosing of venetoclax, monitor for evidence of TLS during treatment, and manage abnormalities in serum creatinine, uric acid and electrolytes promptly. For subjects at higher risk (i.e., circulating blasts), more intensive measures should be considered.

Drug interruption for up to 72 hours following transient (i.e., lasting < 48 hours) chemical changes and laboratory TLS may be allowed and will not require a dose reduction. If the TLS has not resolved within 72 hours, then a dose reduction should be considered.

#### **5.4.6 Dose modifications in obese patients**

There is no clearly documented adverse impact of treatment of obese patients when dosing is performed according to actual body weight. Therefore, all dosing is to be determined solely by the patient's BSA as calculated from actual weight. This will eliminate the risk of calculation error and the possible introduction of variability in dose administration. Failure to use actual body weight in the calculation of drug dosages will be considered a major protocol deviation. Physicians who are

uncomfortable with administering chemotherapy dose based on actual body weight should not enroll obese patients.

## 5.5 Concomitant therapy

All concomitant medications (including start / stop dates, total daily dose, and indication) must be recorded in the subject's source documentation as well as in the appropriate pages of the eCRF. This includes also carrier solution of chemotherapy, hydration, antiemetic therapy, and contrast media, which might be administered during assessments.

For subjects at risk for developing a tumor lysis syndrome (TLS), TLS prophylaxis according to standard local practice with (aggressive) hydration, allopurinol, and/or rasburicase is recommended.

### Not permitted:

General guidelines regarding excluded, cautionary and allowed medications are summarized in [Table 7](#).

Table 7: Excluded and Cautionary Medications and Dietary Restrictions

(See [Appendix 1](#) for Examples of the Medications)

Excluded Foods within 3 days prior to enrolment, During Ramp-Up and Throughout Study:

 
• Grapefruit and grapefruit products
 
• Seville Oranges (including marmalade containing Seville oranges)
 
• Starfruit
 

Excluded Medications During Escalation phase:

 
• Strong and moderate CYP3A inhibitors
 
• Strong and moderate CYP3A inducers
 

Cautionary during Expansion phase and Maintenance

 
• Warfarin*
 
• CYP3A inducers
 
• Strong, moderate and weak CYP3A inhibitors. In case of co-administration of venetoclax and strong and moderate CYP3A inhibitor, a dose reduction of venetoclax is necessary (see Table 8 and 9)
 
• P-gp substrates
 
• BCRP substrates
 
• OATP1B1/1B3 substrates
 
• P-gp inhibitors
 
• BCRP inhibitors
 

\* Closely monitor the international normalized ratio (INR).

A sample list of excluded medications and cautionary medications that fall into the categories can be found in [Appendix 1](#). It is not possible to produce a 100% exhaustive list of medications that fall into these categories, so if in question, please refer to the appropriate product label.

**Note:** In patients with suspected fungal infection during venetoclax days, treatment with caspofungine or liposomal amphotericin B is recommended.

#### Expansion Phase:

For the phase 2 part of the protocol, the below dose modification according to the following [Table 8](#) is recommended in case of co-administration with strong / moderate CYP3A inhibitors.

Table 8: Venetoclax in case of strong and moderate CYP3A inhibitors

Inhibitors	Initiation and Ramp-Up	Venetoclax Daily Dose (after Ramp-Up)
Strong CYP3A inhibitor	Day 1 – 10 mg Day 2 – 20 mg Day 3 – 50 mg Day 4 – 100 mg or less	100 mg or less
Moderate CYP3A inhibitor (reduce the Venetoclax dose by at least 50%)	Day 1 – 20 mg Day 2 – 50 mg Day 3 – 100 mg Day 4 – 200 mg	200 mg

